6. DATA CONVENTIONS

The following analysis conventions will be used in the statistical analysis.

For categorical variables, patients with missing data are not included in calculations of percentages unless otherwise specified. When relevant, the number of patients with missing data is presented.

6.1. Definition of Baseline for Variables

Unless otherwise specified, the baseline assessment for all measurements will be the latest available valid measurement prior to randomization.

6.2. Data Handling Conventions for Efficacy Data

Missing data items for questionnaires

WOMAC scores will be computed when one pain item, one stiffness item, or at most 3 physical function items are missing. The missing items will be imputed by the mean of available items within the same subscale. The scores will be set to missing if more items are missing.

6.3. General Data Handling Conventions

Date of last dose of study treatment

The date of the last injection is equal to the last date of administration reported on injection administration case report form page, or missing if the last administration date is unknown.

Handling of Adverse Event and Injection Site Reaction Severity

If the severity of a TEAE is missing, it will be classified as “severe” in the frequency tables by severity of TEAEs.

Handling of Adverse Event Relatedness

If the assessment of relationship of a TEAE to the study drug or study conduct is missing, it will be classified as “related”.

Handling of Adverse Events or Concomitant Medications with missing or partial start date/time

If the start date of an AE or concomitant medication is incomplete or missing, it will be assumed to have occurred on or after the intake of study medication, except if an incomplete date (eg, month and year) clearly indicates that the event started prior to treatment. Thus, if the AE does not clearly indicate that the AE started prior to treatment or after the TEAE period, the AE will

be classified as “treatment-emergent”. This is for classification purposes in the frequency tables and will not be used in the listings.

Handling of Adverse Events or Concomitant Medications with missing or partial end date/time

When only year is present, missing AE/concomitant medication end day and month will be imputed to the earlier of (study end date, 31DECYYYY).

When both month and year are present, missing AE/concomitant medication end date will be imputed to the last day of the month.

There will be no attempt to impute completely missing AE/concomitant medication end dates. Events with an end date missing will be assumed to be ongoing at the time of data cut off.

Handling of Adverse Events classification with missing or partial date/time of first study drug administration

When the date and time of first study drug dose is missing, the date of randomization will be used as the start date for classification of AEs.

When the time of the first study treatment dose is missing, all AEs that occurred on the date of the first study drug dose will be considered as TEAEs.

Missing/Incomplete Medical history dates

Medical history start dates are used to determine the duration of OA at baseline per eCRF data. Completing missing medical history dates will not imputed. Missing month will be imputed to January and missing day will be imputed to the first day of the month.

Laboratory Safety Variables below LLOQ or above ULOQ

For central laboratory data below the lower limit of quantification (LLOQ), half of the lower limit value (i.e., LLOQ/2) will be used for quantitative analyses.

Missing laboratory, ECG, vital sign, physical exam, neurological exam

No imputations for missing laboratory data, ECG data, vital sign data, physical examination, or neurological examination data will be made.

Handling of Potentially Clinically Significant Abnormalities

If a patient has a missing baseline value they will be grouped in the category “normal/missing at baseline”.

For PCSAs with 2 conditions, one based on a change from baseline value and the other on a threshold value or a normal range, with the first condition being missing, the PCSA will be based only on the second condition.

For a PCSA defined on a threshold and/or a normal range, this PCSA will be derived using this threshold if the normal range is missing; eg, for eosinophils the PCSA is >0.5 GIGA/L or >ULN if ULN \geq 0.5 GIGA/L. When ULN is missing, the value 0.5 should be used.

Measurements flagged as invalid by the laboratory will not be summarized or taken into account in the computation of PCSA values.

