### 6.2.3. Pre-Randomization Period (7 to 10 days)

Following the screening period, patients will complete a 7 to 10 day pre-randomization period. Patients who are not participating in the sub-study will complete the pre-randomization visit as a telephone contact. Sub-study patients will return to the clinic for a pre-randomization visit 7 to 10 days before the randomization visit. During the pre-randomization period, all patients will be instructed to stop using their standard-of-care pain medications and to use only paracetamol/acetaminophen as rescue treatment. In addition, sub-study patients should

discontinue use of paracetamol/acetaminophen 24 hours prior to the start of the randomization visit (baseline).

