### 9.6. Additional Statistical Data Handling Conventions

The following analysis and data conventions will be followed:

General rules for handling missing data:

- If the start date of an AE or concomitant medication is incomplete or missing, it will be assumed to have occurred on or after the intake of study medication, except if an incomplete date (eg, month and year) clearly indicates that the event started prior to treatment. If the partial date indicates the same month or year of the intake of study medication date, then the start date by the study medication intake date will be imputed, otherwise, the missing day or month by the first day or the first month will be imputed.
- No imputations will be made for missing laboratory data, ECG data, vital signs data, or physical examination data.

Visit windows:

- Assessments taken outside of protocol allowable windows will be displayed according to the CRF assessment recorded by the investigator.

Unscheduled assessments:

- Extra assessments (laboratory data or vital signs associated with non-protocol clinical visits or obtained in the course of investigating or managing AEs) will be included in listings, but not summaries. If more than 1 laboratory value is available for a given visit, the first observation will be used in summaries and all observations will be presented in listings.

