4.3. Prior/Concomitant Medications and Procedures, Prohibited Medication

Medications/Procedures will be recorded from the day of informed consent until the End of Follow-up Clinic Visit. Medications will be coded to the Anatomical Therapeutic Chemical (ATC) level 2 (therapeutic main group) and ATC level 4 (chemical/therapeutic subgroup), according to the latest available version of WHO Drug Dictionary (WHODD). Patients will be counted once in all ATC categories linked to the medication.

Medication/Procedure Classifications

Prior medications/procedures are defined as medications/procedures starting prior to the first dose of study drug.

Concomitant medications/procedures are defined as medications/procedures starting prior to or during each respective on-treatment period (as defined in Section 5.8) and ending during or after the respective on-treatment period.

Post treatment medications/procedures are medications/procedures starting after the on-treatment period (as defined in Section 5.8).

Prohibited Medication

Patients were required to discontinue all non-study pain medication (oral or topical; except up to 150 mg/day of aspirin/5-ASA, which is permitted for cardiac prophylaxis, per local guidelines) and opioid analgesic medications, starting at the pre-randomization phone call/visit.

Analgesic medications (including tramadol) were prohibited through week 16. Patients were directed not to take concomitant medications that contain NSAIDs (oral or topical, except up to 150 mg/day of aspirin/5-ASA, which is permitted for cardiac prophylaxis) during treatment period 1. Patients could have taken non-NSAID standard-of-care therapy in addition to study drug, in the event of inadequate pain relief for OA pain, starting after the week 16 visit. Though use of oral NSAIDs should generally be avoided, a limited use is allowed after week 16 for non-OA related pain or fever after week 16. A list of medications containing NSAIDs will be provided in the study reference manual. The dose of oral NSAIDs may be increased and topical NSAIDs may be used during the follow-up period, but no earlier than 16 weeks after the last dose of study drug.

Other excluded drugs during treatment period 1 are:

- Medical marijuana
- Hyaluronic Acid Intra-articular Injections
- Cyclobenzaprine, carisoprodol, orphenadrine, tizanidine

For efficacy sub-study only during treatment period 1:

- Glucosamine sulfate
- Chondroitin sulfate

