5.1.4. Prohibited Medications

Number and percentage of patients with prohibited medications will be descriptively summarized by treatment group, and combined fasinumab based on the SAF-LTS. The tables will be sorted by decreasing frequency of ATC Level 2, ATC Level 4, and preferred term in the combined fasinumab group.

The number of patients with NSAID use during treatment period 1 will be summarized by treatment group, and combined fasinumab. Additionally, the number of patients with more than the limited amount of NSAID use during treatment period 2 will be summarized by treatment group, and combined fasinumab for patients in the SAF-LTS.

Total NSAIDs-use days during each treatment period and follow-up (before AA for patients with AA) will be summarized by treatment group, and combined fasinumab for patients in the SAF-LTS. Additionally, days from last study drug dose to first NSAID dose will be summarized by treatment group, and combined fasinumab for patients in the SAF-LTS.

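### The partial-start-date rules do not test the recorded end date, so an AE that ended before first dose can be tabulated as treatment-emergent and a medication stopped before first dose can fall out of every table

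*SAP*

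**What the plan says.** SAP 6.3 governs AEs and concomitant medications whose start date is incomplete or missing. For such a record "it will be assumed to have occurred on or after the intake of study medication", with one exception: "except if an incomplete date (eg, month and year) clearly indicates that the event started prior to treatment". An AE not clearly placed before treatment, or after the treatment-emergent period, is then classed as treatment-emergent. The scope is limited: "This is for classification purposes in the frequency tables and will not be used in the listings".

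Protocol 9.6 has the same default and exception, and adds a date. If the partial date shares the month or year of first dose, "then the start date by the study medication intake date will be imputed".

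SAP 5.1.3 refers to Section 6.3 for deciding whether a medication with a missing date is prior, concomitant or post-treatment. SAP 4.3 defines those classes. Prior means "medications/procedures starting prior to the first dose of study drug". Concomitant requires a start before or during the on-treatment period and an end during or after it. Post-treatment requires a start after the on-treatment period.

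**The concern.** Assuming the later date is a reasonable default when timing is truly unknown. It is not reasonable when the record itself settles the timing. A complete end date before first dose proves that the AE or medication began before first dose, whatever is missing from its start date. The written rules never consult that end date.

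Such records will exist. Protocol 7.4.1 collects AEs from consent, and protocol 5.7 collects medications from screening, including those begun earlier. The TEAE definition in SAP 5.1.8.1 does not screen the AEs out: an event that resolved before first dose is not present at baseline, so it passes that test.

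Two outputs are at stake. Some resolved pre-treatment AEs could enter the TEAE tables. Some medications stopped before first dose, long-standing analgesics among them, could be missing from the prior-medication table without appearing anywhere else.

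**Working it through.** The plan states no figure for this point, so the check is to run test records through the rules as written. First dose is set at 20 Jun 2018.

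**AEs with a complete end date of 10 Jun 2018**

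| Recorded start | SAP 6.3 class | Protocol 9.6 start | True timing |
|---|---|---|---|
| Jun 2018 | treatment-emergent | 20 Jun 2018 | pre-treatment |
| 2018 | treatment-emergent | 20 Jun 2018 | pre-treatment |
| missing | treatment-emergent | on or after 20 Jun 2018 | pre-treatment |
| May 2018 | pre-treatment | before first dose | pre-treatment |
| 2017 | pre-treatment | before first dose | pre-treatment |

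The first three rows are misclassified. In the first two, protocol 9.6 gives a start 20 − 10 = 10 days after the recorded end.

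**Medication with start missing and a complete end date of 12 Jun 2018**

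- Prior? The start is assumed to be on or after 20 Jun, so no.
- Concomitant? The end, 12 Jun, is before 20 Jun, so no.
- Post-treatment? Nothing places the start after the on-treatment period, so no.

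The record has no class. The same holds if the start is recorded as Jun 2018 or 2018.

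**With an end-date test added**, the first three AEs become pre-treatment and the medication becomes prior. The last two AE rows do not change.

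**How often a missing day leads to the error.** The documents do not give the number of partial dates, so only a conditional share can be shown. Assumptions: AE onset is uniform over the 40 days before first dose (up to 30 days of screening plus up to 10 of pre-randomization), first doses are spread evenly over a 365-day year, and each AE ends D days after onset. The error needs onset k days before first dose with k > D (so that it has ended) and in the same calendar month. In a month of L days, L − k first-dose days meet the month condition. Summing over k = D+1 to L−1 gives (L − D)(L − D − 1)/2 per month. The share is the sum over the twelve months divided by 365 × 40 = 14,600.

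- D = 3: 7 × 378 + 4 × 351 + 300 = 4,350; 4,350/14,600 = 30%
- D = 7: 7 × 276 + 4 × 253 + 210 = 3,154; 3,154/14,600 = 22%
- D = 14: 7 × 136 + 4 × 120 + 91 = 1,523; 1,523/14,600 = 10%

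These are shares of pre-treatment AEs that already lack a start day. They are not shares of all AEs or of patients.

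**The case against.** The best defence is in the SAP's own wording. Its closing sentence asks whether the AE, not just its start date, clearly indicates onset before treatment. A programmer could fairly say that a complete end date before first dose does so. That may well happen in practice. But the exception itself speaks only of an incomplete date, and the end-date test is not written down. The reading also does nothing for medications. A second defence is that the impossible start date arises only from protocol 9.6, since SAP 6.3 classifies without imputing a start, and protocol Section 9 describes itself as the basis for the SAP. That is correct, but the misclassification occurs under the SAP rule alone. A third is that the later-date default is deliberate worst-case handling, in line with the same section's treatment of missing severity as severe and missing relatedness as related. That defends the default where timing is unknown, not where the end date settles it.

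A reader might infer something stronger: that patients who complied with the washout will be counted under "number of patients with NSAID use during treatment period 1". The documents do not support this.

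- An analgesic with a complete stop date before first dose fails the SAP 4.3 definition of concomitant, so its end date is used there.
- A stop recorded only by month and year is a different matter: "missing AE/concomitant medication end date will be imputed to the last day of the month". For a stop 7 to 10 days before first dose, the same calendar month is shared in (365 − 12 × 7)/365 = 77% to (365 − 12 × 10)/365 = 67% of cases, and the imputed end then passes first dose. But this is an ordinary conservative convention, and nothing shows that such partial stops are common.
- The washout, when "all patients will be instructed to stop using their standard-of-care pain medications", is tied to a scheduled contact at which protocol Table 1 also reviews concomitant medications, so its stop dates are plausibly well recorded.
- SAP 5.1.4 gives no date algorithm for the period 1 count. The destructive arthropathy and joint replacement sensitivity analysis in SAP 5.1.8 excludes NSAID users over the whole trial, which includes limited use permitted after week 16.

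Nor is analgesic history lost. Protocol 6.3.1.3 records OA medication history on its own form, and SAP 4.1 summarizes analgesic intolerance and inadequate relief at baseline.

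**Conclusion.** Wrong as written, minor. For an AE with a missing start, or one known only to the month or year of first dose, the rules give a treatment-emergent classification even when the recorded end date rules it out. For a medication with the same pattern of dates they give no classification at all. This follows from the text and needs no assumption about rates.

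The size is unknown and probably small. It depends on how many records combine a partial or missing start with a complete end before first dose, which the documents do not report. The 10% to 30% range applies only to pre-treatment AEs without a start day, under the assumed onset pattern and durations. The listings are outside the rule's scope. The rule is the same for all arms, so there is no evident reason for it to favour one arm. The case for changing it is that the tables should not contradict dates already in the database.

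**What to change.** In SAP 6.3, extend the exception so that a recorded end date before first dose also counts as showing an earlier start. State that such AEs are pre-treatment and such medications are prior, and that no start date is ever imputed later than a recorded end. Bring protocol 9.6 into line. Until that is amended, SAP 1.2.4, which lists departures from the protocol's statistical section, can record the change.

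The cost is about two sentences and a small programming check before database lock. There is no evident downside, because the change affects only records whose own dates contradict the default.

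Reporting the period 1 NSAID count a second time, without records whose only on-treatment evidence is an imputed end date, is at most an optional extra. It would miss true continuing users with partial stop dates, so it should not replace the planned count.

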6.4. Visit Windows

By-visit analysis (including efficacy, laboratory data, vital signs, ECG, ADA) will be summarized by the nominal visit number. Assessments taken outside of protocol allowable windows will be displayed according to the case report form (CRF) assessment recorded by the investigator. For assessments without a nominal visit number such as Unscheduled, EOT, and EOS assessments, a visit number will be assigned based on the actual visit date using the study day analysis window based on the targeted visit study day in [Appendix 11.1 Table 2](#) Schedule of Events.

The following visit windows will be used to map the unscheduled visits, early end of treatment visits, early study termination visits and daily electronic dairy entries, based on the study day:

Visit No.	Visit	Targeted Study Days*	Analysis Window in Study Days
1	Screening	Day -30 to Day -11	≥ -30 and ≤ -11
2	Pre-randomization Phone Call	Day -10 to -7	-10 to -1
3	Baseline	1	≤ 1
	Week 1 (efficacy sub-study)	8	[2, 11]
	Week 2 (efficacy sub-study)	15	[12, 22]
4	Week 4	29	[23,43](efficacy substudy);[2,43] (LTS)
5	Week 8	57	[44,71]
6	Week 12	85	[72,99]
7	Week 16	113	[100,127]
8	Week 20	141	[128,155]
9	Week 24	169	[156,183]
10	Week 28	197	[184,211]
11	Week 32	225	[212,239]
12	Week 36	253	[240,267]
13	Week 40	281	[268,295]
14	Week 44	309	[296,323]
15	Week 48	337	[324,351]
16	Week 52	365	[352,393]
17	Week 60	421	[394,463]
18	Week 72	505	≥ 464

*Study days are calculated from the first dose of study drug (Day 1).

If multiple measurements occur within the same visit window, the following rules will be used to determine the analysis value:

- When multiple valid measurements occur within the same visit window, the one closest to the target study day will be used in the analysis.
- When multiple valid measurements occur within equal distance from the target study day, the value after the target study day will be used in the analysis.

Both scheduled and unscheduled measurements will be considered for determining abnormal/PCSV values from laboratory, vital sign or ECG as well as the baseline values.

6.5. Unscheduled Assessments

The determination of baselines and values at the end of treatment for both efficacy and safety variables will be based on available assessments of scheduled and unscheduled visits. For by visit summaries, unscheduled visit will be mapped to a visit using the visit windows described in Section [6.4](#) and then included in the by-visit summaries.

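### SAP 6.4 and 6.5 put unscheduled laboratory and vital-sign values into by-visit summaries against protocol 9.6, and let a triggered retest replace the scheduled value

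*SAP*

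**What the plan says.** Protocol 9.6 deals with extra assessments: laboratory or vital-sign values from non-protocol clinic visits, or obtained while an AE is investigated or managed. These "will be included in listings, but not summaries". For laboratory tests it adds a rule for duplicates: "If more than 1 laboratory value is available for a given visit, the first observation will be used in summaries".

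SAP 6.5 takes a different line: "For by visit summaries, unscheduled visit will be mapped to a visit using the visit windows described in Section" (the reference is to SAP 6.4). Values mapped in this way enter those summaries. SAP 6.4 opens by saying that by-visit analyses follow the nominal visit number, and that assessments without one (unscheduled, EOT, EOS) are assigned a visit by study-day window. Its rule for duplicates is: "When multiple valid measurements occur within the same visit window, the one closest to the target study day will be used in the analysis". If two values are equally distant, the one after the target day is used. Nothing in the rule prefers the scheduled value.

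SAP 1.2.4 is the place for changes from the protocol's statistical section. It lists one dropped exploratory endpoint, time to adjudicated and destructive arthropathy, and hs-CRP. It does not mention unscheduled assessments.

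**The concern.** Followed literally, the two documents produce different by-visit laboratory and vital-sign tables, and the SAP does not say that it departs from the protocol.

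The difference matters because unscheduled values are not a random sample. Protocol 6.2.12 gives repeat testing after abnormal results and AE follow-up as reasons for unscheduled visits. The laboratory section, 6.3.4.11, requires significantly abnormal tests to be repeated. Section 7.6.1.2 brings patients with orthostatic hypotension back in 1 to 10 days. Whether a patient has a second value in a window therefore often depends on the first value or on an AE.

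Under the SAP, such a value can stand in for the scheduled one. Change in safety laboratory values is a named part of the primary safety endpoint (protocol 8.2, SAP 4.5.1), and SAP 5.1.8.3 and 5.1.8.4 summarise laboratory and vital-sign change visit by visit. If triggered testing is more frequent in one arm, the distortion need not cancel between arms.

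**Working it through.** The documents attach no figure to this point, so there is nothing to reproduce. The check compares the rules and then works through what the SAP rule does.

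**Rules side by side**

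| Situation | Protocol 9.6 | SAP 6.4 and 6.5 |
|---|---|---|
| Extra laboratory or vital-sign value | Listing only | Mapped to a window and summarised |
| Several laboratory values at a visit or in a window | First | Closest to target day; tie goes to the later value |
| Scheduled value missing, extra value present | Visit stays missing in summaries | Extra value fills the visit |

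**Worked example, week 8** (target day 57, analysis window days 44 to 71, SAP 6.4)

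- Scheduled on day 52, 5 days off. Retest on day 58, 1 day off. The retest is used.
- Scheduled on day 54, 3 days off. Retest on day 60, 3 days off. The tie goes to the later value, so the retest is used.
- Scheduled on day 57. No value from another day can displace it.

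**How often a later retest wins, given that there is one**

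Inputs: scheduled visit at offset s from −7 to +7 days (the visit window in protocol Table 1), and a retest g = 1 to 10 days later (the interval in protocol 7.6.1.2, used here for any retest). Equal weight on each day is an assumption.

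The retest wins if |s + g| < |s|, or if the two distances are equal with the retest later. For an early visit (s < 0) this means g ≤ 2|s|, so the count is min(2|s|, 10). For s ≥ 0 a later retest never wins.

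- s = −1 to −7: 2 + 4 + 6 + 8 + 10 + 10 + 10 = 50.
- All visits: 50 / (15 × 10) = 50/150 = 33%.
- Early visits only: 50 / (7 × 10) = 50/70 = 71%.
- Visits kept within ±3 days: (2 + 4 + 6) / (7 × 10) = 12/70 = 17%.
- Under the protocol rule: 0% by construction.

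The result is the same for the week 4, 8, 16, 32 and 52 windows. If the unscheduled value may instead fall on any other day of the analysis window, before or after the scheduled visit, it wins in 105 of 405 combinations (26%) at weeks 8 and 16, and in 105 of 615 (17%) at week 4 (LTS window) and week 52.

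**Effect on a visit mean**

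Shift = q × D. Here q is the share of all values at the visit that are displaced, and D is the mean of retest minus displaced scheduled value, in SD units and with either sign. Neither is in the documents. Assumed ranges:

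| q | D = 0.5 SD | D = 1 SD | D = 2 SD |
|---|---|---|---|
| 1% | 0.005 | 0.01 | 0.02 |
| 5% | 0.025 | 0.05 | 0.10 |
| 10% | 0.05 | 0.10 | 0.20 |

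With one third of retests winning, q = 1% needs 0.01 × 3 = 3% of patients to have a retest at that visit, and q = 10% needs 0.10 × 3 = 30%. The upper rows therefore require frequent retesting.

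**The case against.** The strongest reply is that the consequence is limited. The affected tables are descriptive. The modelled primary safety comparisons are Poisson incidence rates (SAP 5.1.7.1), which this rule does not touch. PCSV analyses use all scheduled and unscheduled values (SAP 5.1.7 and 6.4), so abnormal results are not lost. Displacement also needs an extra value in the same window that is closer to target, or tied and later. All of this stands, and it keeps the point modest.

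The opening sentence of SAP 6.4, on nominal visit numbers, might be read as protecting scheduled values. It says which visit a value belongs to, but not which of two values in a window is used. The duplicate rule does decide that, without preferring the scheduled value, and 6.5 expressly includes unscheduled ones.

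Mapping also has some use: a valid redraw can fill a visit whose scheduled sample was missing or invalid, since SAP 6.3 imputes nothing. That is a fair reason to allow filling under a stated rule. It is not a reason to allow displacement.

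A reader might infer that windows without a scheduled test, such as chemistry at week 12, would be populated almost entirely by triggered values. The documents do not support this. SAP 5.1.8.3 summarises laboratory change to each scheduled assessment time, which may keep such windows out of the tables. SAP 5.1.7 also restricts laboratory and vital-sign descriptive statistics to the period from first dose to 28 days after end of treatment, which excludes the week 60 and week 72 windows for a patient treated to week 48 (day 337 + 28 = day 365; the week 60 window opens on day 394).

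**Conclusion.** The contradiction is real and undeclared. Under the SAP as written, a result-triggered or AE-triggered value can replace a scheduled one, most readily when the scheduled visit was early, or fill a missed one, in the descriptive by-visit laboratory and vital-sign change tables. Given a retest 1 to 10 days later, it wins in about a third of day combinations. That figure rests on equal weighting of days and applies only to patients with a retest.

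The shift in any visit mean cannot be calculated from the documents and is probably small unless retests are common or unbalanced between arms.

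Two stronger readings are tempting. One is that the by-visit safety changes as a whole become outcome-selected and inflated in the arm with more AEs. The documents do not support this: only patients with extra values are affected, and the direction is open. A retest that has returned to normal can hide an abnormal scheduled value, while an AE-triggered value can inflate change. The other is that the full change from baseline in a triggered value is artefact. When a value is displaced, only the difference between it and the scheduled value is, and after an abnormal test that scheduled value is often already raised.

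AE and AESI incidence rates and PCSV counts are unaffected. The protocol's exclusion names laboratory and vital-sign data, so the contradiction does not extend to ECG.

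**What to change.** In SAP 6.4 and 6.5, state that:

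- by-visit descriptive laboratory and vital-sign summaries use the scheduled (nominal-visit) value, taking the first observation for laboratory tests, together with re-mapped EOT and early-termination visits;
- an unscheduled value never displaces a valid scheduled one;
- unscheduled values continue to feed baseline, PCSV analyses and listings, as the SAP already provides.

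If an unscheduled value is to be allowed to fill a visit whose scheduled value is missing or invalid, say so and record it in SAP 1.2.4 as a departure from protocol 9.6. The same entry should mention the PCSV tables. Read literally, the protocol keeps extra values out of all summaries, so this proposal reconciles the two documents and does not simply restore the protocol wording.

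The cost is a few sentences of SAP text and slightly fewer values in the by-visit tables. No data collection changes.
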